5.3 Exclusion Criteria for the Subsequent Vaccination

If any of the following 1)-3) occurs, it's forbidden to continue vaccination, but other study procedure can be continued according to the investigator's judgement; if the following 4) occurs, the it's up to the investigator to decide whether to vaccinate or not; if the following 5)-6) occurs, the vaccination could be postponed within the required time window.

- 1) Any newly confirmed or suspected autoimmune disease or immunodeficiency disorders;
- 2) Any serious adverse events related to vaccination in this study;
- 3) Severe allergic reactions after vaccination in this study;
- 4) Other reactions (e.g., severe pain, severe swelling, severe activity limitation, persistent high fever, etc.) or factors which are considered to have influence on the vaccination according to the investigator's judgement;
- 5) Various acute disease or acute exacerbation of chronic diseases by the time of vaccination;
- 6) Axillary temperature $\geq 37.3^{\circ}\text{C}$.

5.4 Lifestyle Considerations

- A. Restrictions relating to prohibited and restricted therapy during the study are described in [Section 6.7](#).

B. Participants must agree to follow all requirements that must be met during the study as noted in the inclusion and exclusion criteria.

5.5 Screening Failures

Screen failures are defined as participants who consent to participate in the clinical study but not subsequently randomly received study intervention. A minimal set of screen failure information is required to ensure transparent reporting of screen failure participants and to respond to queries from regulatory authorities. Minimal information includes demography, screen failure details, eligibility criteria.

6. STUDY VACCINATION AND CONCOMITANT THERAPY

6.1 Investigational Vaccines Administered

Arm Name	Arm 1/Arm2/Arm 3
Intervention name	Poliomyelitis Vaccine (Vero cells), Inactivated, Sabin Strains (hereinafter as “sIPV”)
Type	Vaccine
Dose Formulation	Pre-filled syringe or vial with an extractable volume of 0.5 ml
Unit Dose Strengths	15DU/45DU/45DU for serotype I, II, III per 0.5ml
Route of Administration	Intramuscular injection (preferably in anterolateral thigh muscles)
Use	Experimental
Investigational Medical product (IMP)	Yes
Sourcing	Provided by Sinovac
Packaging and Labeling	The study vaccines will be packed in individual participant kits, one kit will be used only by one participant. Each kit will contain single-use syringe or a vial.

6.2 Preparation/Handling/Storage/Accountability

Preparation/Handling/Storage

- The study vaccines should be stored and transported protected from light at approximately 2°C to 8°C. If there is a break in the cold chain, a report should be sent to the sponsor to determine whether the affected supplies can be used or will be replaced. All the affected study vaccine must be quarantined until further instruction from the sponsor is received.
- Only participants enrolled in the study may receive study intervention and only authorized site staff may supply or administer study intervention.
- Study intervention should be prepared and dispensed by an appropriately qualified and experienced member of the study staff (e.g., physician, nurse, physician’s assistant, nurse practitioner, pharmacy assistant/technician, or pharmacist) as allowed by local, state, and institutional guidance. A second staff member will verify the dispensing.

Accountability

The investigator or designee is responsible for study intervention accountability, reconciliation, and record maintenance (i.e., receipt, reconciliation, and final disposition records). All study interventions will be accounted for using a study intervention accountability form/record.

Unused study interventions must be available for verification by the sponsor's site monitor during on-site monitoring visits. Unused study interventions will be destroyed on-site and documented on the Investigational Product (IP) accountability form.

6.3 Measures to Minimize Bias: Randomization and Blinding

Randomization

The enrolled participants will be randomly separated into four groups (i.e., the co-administration group 1, co-administration group 2, staggered administration group 1 and staggered administration group 2) at a 1:1:1:1 ratio. Stratified Blocked Randomization will be carried out, taking the study site as a stratification factor. The independent randomization statistician will use SAS 9.4 software or later versions to generate a randomization code list. In order to minimize the probability of relevant persons being informed of the group, the paper randomization card with numbers will be used. For each eligible participant, after enrollment, the grouping information will be revealed, including the name of the vaccine and the site of vaccination.

Blinding

This study adopted an open-labelled design, it would not be possible to blind the participant group. However, during blood collection, it should be guaranteed the Phlebotomist/Study Nurse/Medical Technologist are not aware of the participant group to reduce bias. In addition, lab personnel will be completely blind during the laboratory assessment as each sample will be labelled with unique ID code without grouping information.

6.4 Study Treatment Compliance

Study interventions will be administered by the investigator or designee, and the date and time of vaccine administration and the injection location will be recorded in the eCRF.

The study site is responsible for ensuring that participants comply with the study windows allowed. If a participant missed a visit, every effort should be made to contact the participant and complete a visit within the defined visit window. If a participant does not complete a visit within the time window, that visit will be classified as a missed visit and the participant will continue with subsequent scheduled study visit. All safety requirements of the missed visit will be captured and included in the subsequent visit.

6.5 Dose Modification

Not applicable.

6.6 Treatment of Overdose

For this study, any dose of the study vaccines greater than the assigned dose will be considered as overdose. The sponsor does not recommend specific treatment for an overdose.

In the event of a known overdose, the investigator should:

- Contact the medical monitor immediately.
- Closely monitor the participant for AE/SAE.
- Document the quantity of the excess dose in the source document.
- Any overdose will be tracked as protocol deviations and reported to the IRB/IEC and Sponsor.

6.7 Concomitant Medications and Therapies

➤ Permitted During the Study

- If an AE occurs during the study period, necessary drug therapy and medical treatment are allowed;
- If severe allergic reaction or life-threatening reaction occur, first aid measures should be taken immediately;
- The investigator should record detailed information on any concomitant medicine during the study, including name, doses, duration, etc.
- Participants will not be prohibited from receiving vaccine for an emergency medical indication, such as rabies;
- Administration of any vaccines other than the study vaccine during the study should be recorded in detail, including name, dosage and usage, date, etc.

➤ **Prohibited During the Study**

- Participants are prohibited to receive vaccines other than the study vaccine throughout the study, except for an emergency medical indication as abovementioned;
- Refer to [Section 5.2](#) for further details of prohibited therapy.

7. DELAY/DISCONTINUATION OF STUDY VACCINATION AND PARTICIPANT DISCONTINUATION/WITHDRAWAL

7.1 Participants Discontinuation/Withdrawal from the Study

A participant may withdraw from the study at any time at his/her own request. A participant will be withdrawn from the study for any of the following reasons:

- Guardian's decision;
- An intolerant AE, whether related to the investigational product or not;
- The physical condition of the participant is not suitable for the study;
- Any abnormal clinical symptoms, the causality to the investigational product will be decided by the investigator, who will decide the participant's withdrawal;
- The investigator decision for any other reasons.

The investigator or designee will attempt to contact those guardians of participants who do not return for scheduled visits or follow-up. The reason for withdrawal will be recorded in the eCRF. If withdrawal is due to an AE after vaccination, appropriate follow-up visits or medical care will be arranged, with the agreement of the participant, until the AE has resolved. In any circumstance, every effort should be made to document participant outcome, if possible. If a participant withdraws from the study, data and blood samples collected before their withdrawal will still be used in the analysis. Storage of blood will continue unless the participant specifically requests otherwise.

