8.1 Immunogenicity Assessments

8.1.1 Blood Collection and Laboratory Testing

Blood samples from all participants will be obtained for humoral immunogenicity testing at the visits specified in the SoA. All the serum samples for the immunogenicity assay will be sent to the assigned laboratory for analysis. In terms of antibody testing, the laboratory method and definition of immune response are summarized in the following table:

Table 5 Laboratory Testing Method and Definition of Immune Response

Antigens	Method	Category of antibody	Cutoff	Definition of immune response
Poliovirus type 1-3	Micro-neutralization	Neutralizing antibody	≥1:8**	Seroconversion: pre-vaccination titer <1:8 and post vaccination titer ≥1:8, or 4-fold titer increase in case that pre-vaccination titer ≥1:8 Sero-protection: ≥1:8
DT	ELISA	IgG	≥0.1 IU/ml**	Sero-protection: ≥0.1 IU/ml
TT	ELISA	IgG	≥0.1 IU/ml**	Sero-protection: ≥0.1 IU/ml
PT	ELISA	IgG	≥20EU/ml	Seropositivity: ≥20EU/ml
FHA	ELISA	IgG	≥20EU/ml	Seropositivity: ≥20EU/ml
PRN	ELISA	IgG	≥20EU/ml	Seropositivity: ≥20EU/ml
HepB	ELISA	IgG	10 mIU/ml**	Sero-protection: ≥10 mIU/ml
Hib	ELISA	IgG	0.15µg/mL**	Sero-protection: ≥0.15µg/mL
Pneumococcal*	ELISA	IgG	0.35µg/mL**	Sero-protection: ≥0.35µg/mL

*The following serotypes will be detected in this study: 1, 5, 6B, 14, 19F

**Cut-off accepted as indicative of protection.

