8.5.5 Safety Follow-up

All participants will be observed for 30 minutes on site after the last injection in each vaccination visit. Diary cards will be distributed to guardians of participants to record AEs from the time of first vaccination to 28 days after last vaccination. Investigators should explain the judgment, measurement, recording, precautions and reporting method of AEs. Solicited local and systemic AE observation is carried out within 7 days after vaccination. Guardians of participants are required to closely observe participants' symptoms and temperature and fill the diary every day.

The investigator and designees verify all the AEs reported in the diary card on the 14th day after vaccination through face-to-face interviews or telephone calls; The investigator and designees verify the AEs on the 28th day after vaccination through face-to-face interview (only applicable for co-administration group and last dose of staggered administration groups).

The participants are informed to record the AEs at any time. Acute allergic reactions, AEs with severity of grade 3 and above, and SAEs should be reported to the investigator in a timely manner. SAEs will be collected from the time of first vaccination to 28 days after the last vaccination. After the investigators are informed, they should conduct investigation, verification and follow-up until the AE has resolved, and finally complete the detailed investigation and follow-up records, which should include the following contents:

- Participant's identified information
- Description of AE's start time and end time of AEs
- Seriousness of AEs

- Severity level
- Relationship to vaccination
- Laboratory testing results
- Treatment measures
- Outcome of the AEs

Follow-up by the investigator continues throughout and after the active collection period and until the AE or SAE or its sequelae resolve or stabilize. Follow-up information will include a description of the event in sufficient detail to allow for a complete medical assessment of the case and independent determination of possible causality. Any information relevant to the event, such as concomitant medications and illness, must be provided.

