- Schedule an appointment for the participant to return for the next study visit;
- Complete the source documents and eCRFs.

Visit 4- Safety-V3+14 (+3) days

- Verify the AEs, and the completeness of the Diary Card; this visit will be conducted by telephone, remotely;
- Verify concomitant vaccines (non-study vaccinations) and/or concomitant medicine;
- Verify details of any of the prohibited medications received by the participant;
- Ask the participant to contact the site staff or investigator if a medically attended event (e.g., doctor's visit, emergency room visit) or hospitalization occurs;
- Schedule an appointment for the participant to return for the next study visit.

Visit 5- Third Vaccination-V3+28 (+7) days

- Review the AEs of participant's diary card data through a face-to-face interview;
- Collect stop dates of any AEs ongoing on the last day that the diary card was completed and record stop dates in the eCRF if required;
- Record concomitant vaccines (non-study vaccinations) and/or concomitant medicine;
- Collect the Diary Card from participants;
- *The participant's axillary temperature will be measured;*
- Check the vaccination discontinue/postpone rules;
- Site staff members(s) will dispense/administer the study intervention;
- Site staff must observe the participant for at least 30 minutes after study intervention administration for any immediate or acute reactions. Record any acute reactions (including time of onset) in the participant's source documents and on the AE page of the eCRF, and on an SAE form as applicable;
- New Diary Card will be provided to participants, and confirm instructions on diary card completion;
- Ask the guardians of participants to contact the site staff or investigator if a medically attended event (e.g., doctor's visit, emergency room visit) or hospitalization occurs;
- Schedule an appointment for the participant to return for the next study visit;
- Complete the source documents and eCRFs.

Visit 6-Safety-V5+14 (+3) days

- Verify the AEs, and the completeness of the Diary Card; this visit will be conducted by telephone, remotely;
- Verify concomitant vaccines (non-study vaccinations) and/or concomitant medicine;
- Verify details of any of the prohibited medications received by the participant;
- Ask the participant to contact the site staff or investigator if a medically attended event (e.g., doctor's visit, emergency room visit) or hospitalization occurs;

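### Section 7.1 takes an infant out of the whole study for an intolerant AE or unsuitable condition; stopping vaccination only, as in 5.3, would keep the single post-vaccination titre

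*Protocol*

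**What the plan says.** Protocol 7.1 introduces its list of reasons with "A participant will be withdrawn from the study for any of the following reasons". Two of them are "An intolerant AE, whether related to the investigational product or not" and "The physical condition of the participant is not suitable for the study". A later item, abnormal clinical symptoms, leaves the decision to the investigator; these two items do not say so. After an AE withdrawal, follow-up or care is arranged until the event resolves, and "data and blood samples collected before their withdrawal will still be used in the analysis". Neither 7.1, the schedules of activities nor section 8.6 plans an exit draw.

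Protocol 5.3 deals with overlapping events differently. For new immune disease, a vaccination-related SAE or a severe allergic reaction, "it's forbidden to continue vaccination, but other study procedure can be continued according to the investigator's judgement". For other marked reactions (item 4) the investigator decides whether to vaccinate again.

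In C1 and S1 blood is taken at baseline and at Visit 7, 28 (+7) days after Visit 5 (Protocol 8.6.1 and 8.6.2). In C1 the third sIPV dose falls at "Visit 5- Third Vaccination-V3+28 (+7) days". In S1 Visit 5 also gives the third sIPV dose, and Visit 6 the third routine dose. The FAS needs one dose and a valid baseline result (Protocol 9.2, SAP 6). A missing post-vaccination titre is filled by LOCF (Protocol 9.6; SAP 7.9, for the FAS). Seroconversion is a move from below 1:8 to 1:8 or above, or a "4-fold titer increase in case that pre-vaccination titer ≥1:8" (Protocol 8.1.1).

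**The concern.** A related SAE or severe allergic reaction can meet both 5.3 and 7.1. The sections state different consequences and do not refer to each other. Both leave room for judgement, but only 7.1 names leaving the study as the result.

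With one post-vaccination draw, that choice decides whether the primary endpoint is measured at all. If it is not, the FAS inserts a value that can only be a failure. Staff know the group, and the two schedules may produce different reactions, so equal withdrawal cannot be taken for granted. An infant withdrawn after full vaccination but before the draw also leaves the PPS, in either group, for want of a post-vaccination result.

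**Working it through.** **1. What LOCF does.** The only earlier titre is the baseline. With post equal to pre, a titre below 1:8 stays below 1:8, and a titre of 1:8 or above has a fold rise of 1. Neither meets the definition, so each such infant is a non-seroconverter.

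**2. Who is affected.** This can happen in either group, and at any stage before Visit 7. C1 infants who react after Visit 5, and S1 infants who react after Visit 5 or Visit 6, already have three sIPV doses, so the Visit 7 titre they lose is the endpoint itself.

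**3. The plan's own figure.** Inputs (Protocol 9.1): 90% in both groups, margin 10 points, one-sided 0.025, power 1 − 0.20/3 = 93.3%. The Farrington-Manning score formula, with null rates 0.831 and 0.931, gives 231.8, so 232 against the stated 233. That figure is not in dispute.

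**4. Shift per infant.** At most 1/360 = 0.28 points. An assumed excess of four gives 4/360 = 1.11 points. If 10% lack a baseline result (assumed), n = 324 and the shift is 4/324 = 1.23 points.

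**5. Effect on the lower limit.** Unstratified, unpooled Wald limit: d − 1.96 × √[(p₁(1−p₁) + p₂(1−p₂))/n]. Power: Φ[(0.10 + d)/SE − 1.96]. Both take the true rate as 90% in each group and everyone else as measured.

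| n per group | Excess withdrawn (assumed) | 95% lower limit (points) | Power per serotype |
|---|---|---|---|
| 360 | none | −4.4 | 99.4% |
| 360 | 3 in C1 | −5.3 | 98.1% |
| 360 | 4 in C1 | −5.6 | 97.3% |
| 360 | 4 in S1 | −3.4 | – |
| 324 | none | −4.6 | 98.9% |
| 324 | 4 in C1 | −6.0 | 95.2% |

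For four in C1 at n = 360: d = −0.0111, SE = 0.0229, limit = −0.0111 − 1.96 × 0.0229 = −0.056.

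**6. How many would overturn the result.** Smallest C1 excess that takes the limit to −10 or below:

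| n per group | True rate 90% | 95% | 99% |
|---|---|---|---|
| 360 | 19 | 22 | 26 |
| 324 | 16 | 19 | 23 |

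**7. How many to expect.** The documents give no AE-withdrawal rate. The nearest figure is no vaccine-related SAE in the earlier trials, with 739 infants given the market dose (Protocol 2.2.3). Taking 0 of 739, the one-sided 95% upper bound is 1 − 0.05^(1/739) = 0.40%, or about 0.00405 × 720 = 2.9 infants in C1 and S1 together. An intolerant AE of any causality is a wider class and could be more frequent.

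**8. Timing of a retained draw.** With existing windows, Visit 7 falls 84 to 105 days after Visit 1 in C1 (3 × 28 to 3 × 35) and 84 to 103 days in S1 (4 × 14 + 28 to 4 × 17 + 35). An infant stopped after dose 2 would be drawn 56 to 70 days after that dose in C1 (28 + 28 to 35 + 35) and 56 to 69 in S1 (14 + 14 + 28 to 17 + 17 + 35).

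**The case against.** - **Section 5.3 already covers the likeliest events, and the wording of 7.1 is itself a judgement.** This stands in part. An investigator can read 5.3 as the specific rule, and Protocol 6.4 keeps an infant who misses a visit. But once an AE is judged intolerant, 7.1 names only one outcome.
- **The root problem is baseline LOCF.** This stands. Rewording 7.1 does nothing for guardian refusal, loss to follow-up or failed draws, and the plan allows about 15% dropout and 10% blood-collection failure. Those losses dominate. If 15% were carried forward in both groups, the rates would be 0.90 × 0.85 = 76.5% and the starting limit −6.2 rather than −4.4; four excess infants in C1 would make it −7.4.
- **A reader might infer bias towards non-inferiority**, because S1 has six vaccination visits. The documents do not show it. Excess withdrawal in C1 works against non-inferiority, excess in S1 works towards it, and equal numbers largely cancel.
- **A reader might infer a serious loss of power.** Withdrawal of 5% in C1 and 1% in S1 would give a difference of −3.6 points and 73.3% power, but nothing in the documents supports those rates.
- **A reader might infer that safety data are lost.** The AE that led to withdrawal is followed to resolution, and 8.5.5 says "SAEs will be collected from the time of first vaccination to 28 days after the last vaccination" with no exception for withdrawn infants. The avoidable loss is mainly the titre.

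**Conclusion.** The point holds as a cheap improvement, not as a threat to the primary conclusion. By its wording, 7.1 turns some infants whose response could be measured into FAS failures, where 5.3 would let them stay.

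The size is at most 0.28 points per excess infant at 360 per group, and about 1.1 points for an assumed excess of four, against a margin of 10. No direction of bias is shown. The limits and power rest on assumed excesses, a 90% rate in both groups, no other missing titres and an unstratified Wald interval in place of the planned stratified one.

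The gain is firmest for infants with all three sIPV doses. For partly vaccinated infants, a measured titre is better information than a carried-forward baseline, but it is not the protocol endpoint.

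**What to change.** - **Protocol 7.1:** an intolerant AE or unsuitable physical condition leads to discontinuation of study vaccination, with a cross-reference to 5.3 that keeps the investigator's discretion in item 4. Limit study withdrawal to guardian decision, loss to follow-up, or a documented medical reason why visits or draws cannot be done.
- **Schedule:** with guardian agreement, keep the safety visits and the Visit 7 draw. State how Visit 7 is timed when Visit 5 gives no vaccine, since it is anchored to Visit 5.
- **SAP:** add one sentence that a measured Visit 7 titre replaces LOCF in the FAS even if the series is incomplete. It is needed because SAP 5.1 and 7.7 place the endpoint 28 days after the last sIPV dose, and SAP 7.1.3 keeps unscheduled visits out of the tables. Infants with an incomplete series stay out of the PPS.
- **Protocol 6.7:** release infants stopped from study vaccination from the ban on non-study vaccines, so that they can receive their EPI doses. Record any non-study polio vaccine and treat the titre as a treatment-policy value.
- **eCRF:** one field separating vaccination stop from study withdrawal.

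The cost is this short set of edits and a few more visits and draws for some families. For partly vaccinated infants, the titre is not 28 days after dose 3 and may reflect non-study polio vaccine.

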7.2 Lost to Follow-up

A participant will be considered lost to follow-up if he or she repeatedly fails to return for scheduled visits and is unable to be contacted by the study site. The following actions must be taken if a participant fails to return to the clinic for a required study visit:

- The site must attempt to contact the participant's guardians and reschedule the missed visit as soon as possible, counsel the participant on the importance of maintaining the assigned visit schedule and ascertain whether the participant wishes to and/or should continue in the study.
- Before a participant is deemed lost to follow-up, the investigator or designee must make every effort to regain contact with the participant (where possible, telephone calls and, if necessary, a certified letter to the participant's last known mailing address or local equivalent methods). These contact attempts (e.g., dates of telephone calls and registered letters) should be documented in the participant's medical record. A participant should not be considered lost to follow-up until these efforts have been made.
- Should the participant continue to be unreachable, he/she will be considered to have withdrawn from the study.

